## 8.3 Assessment of Potential Risks and Benefits

The risks to the study subjects result from performing the standard urodynamic test and delivering acute PNS from an already active implantable PNS device. Urodynamic testing is a commonly performed, standard of care, procedure used for assessing urinary incontinence and other voiding dysfunctions. Furthermore, the PNS stimulation parameters are within the allowable ranges of the approved stimulation device.

The following activities will be implemented for risk mitigation:

- Only highly experienced health care professional in the field of clinical urology will be selected to perform this study.
- Only subjects meeting the inclusion and exclusion criteria will be enrolled in the study to minimize any pre-disposition to any potential harms.
- The subject's physiologic status will be continuously monitored during the clinically indicated procedure.
- A prophylactic antibiotic will be administered prior to the urodynamic test.

The investigator or fully trained designated study personnel will always be present to conduct the clinical study and may terminate the study at their discretion based on changes in subject condition and study observations.

## 9 STUDY POPULATION

Study subjects will include female patients with an implantable PNS device. To be eligible to participate in this study, an individual must meet all of the inclusion criteria and none of the exclusion criteria listed below.

### 9.1 Inclusion Criteria

1. Women between the ages of 18 and 85 years old, inclusive.
2. Implanted with a neurostimulation device for at least 3 months prior to consent (Medtronic InterStim neurostimulator models 3023, 3058, 97810, or similar;)
3. Implanted with a tined lead that is placed and functional at the pudendal nerve (Medtronic model 3889 or similar)
4. Is capable of understanding clinical study procedures and giving informed consent.
5. Willing and able to visit the clinic for the UDT evaluation (study procedure)

Note: No more than eight subjects having no history of SUI as determined by the investigator.

### 9.2 Exclusion Criteria

1. Medically unstable at time of study and unsafe to undergo urodynamic testing as determined by the investigator
2. Active bladder cancer
3. History of pelvic radiotherapy
4. Active gross hematuria
5. Active symptomatic urinary tract infection (UTI)
6. Active symptomatic uncontrolled bladder instability as determined by the investigator
7. History or symptoms of cystocele, enterocele or rectocele of grade 3 or 4. Per the medical record or as determined by the investigator
8. Presence of an artificial urinary sphincter
9. Women who are pregnant and/or have given birth in the previous 12 months
10. Any medical condition (e.g. Multiple Sclerosis, spinal cord injury, mobility) or uncontrolled chronic disease (e.g. diabetes, renal diseases that requires dialysis) that would interfere with the patient's ability to comply with the protocol and/or may affect the outcome of this study or safety of the subject as determined by the investigator
11. BMI>39

### 9.3 Enrollment

The point of enrollment is defined as the time a participant signs the ICF and meets all the inclusion criteria and none of the exclusion criteria.

### 9.4 Screen Failure

Participants who are consented to participate in this early feasibility clinical trial are considered screen failures if the subject does not meet one or more of the eligibility criteria required for participation. Screen failures will not be assigned to the study procedure and their data will not be included in the data analysis.

Screen failure because of Exclusion criterion #1 (i.e. unstable medical condition) may be rescreened. Rescreened participant should be assigned the same participant number as for the

initial screening.

#### 9.5 Participant Discontinuation/Withdrawal from the Study

Study participants are free to withdraw from participation in the study at any time upon request.

Although Investigators should seek to minimize participant discontinuation or withdrawal from the study except for safety reasons. The PI may discontinue or withdraw a study participant from the study for the following reasons:

- Pregnancy
- Significant study intervention non-compliance
- If any clinical adverse event (AE), or other medical condition or situation occurs such that continued participation in the study would not be in the best interest of the participant
- Disease progression which requires withdraw from participation
- If the participant meets an exclusion criterion (either newly developed or not previously recognized) that precludes further study participation
- The study participant is unable to receive PNS

The reason for participant discontinuation or withdrawal from the study will be recorded on the Study Exit Case Report Form (CRF). Subjects who sign the Informed Consent Form but did not completed the UDT with and without PNS may be replaced.

#### 9.6 Lost to Follow-Up

A participant will be considered lost to follow-up if the participant fails to return for the stimulation visit and is unable to be contacted by the study site staff.

The following actions must be taken if a participant fails to return to the clinic for a required study visit:

- The site will attempt to contact the participant and reschedule the missed visit within one week and counsel the participant on the importance of maintaining the assigned visit schedule and ascertain if the participant wishes to or should continue in the study.
- Before a participant is deemed lost to follow-up, the Investigator or designee will make every effort to regain contact with the participant where possible, three telephone calls, text or any other messaging methods. These contact attempts should be documented in the participant's medical record or study file.

### 10 Data Analysis

This early feasibility study is designed to obtain initial insights into evaluating the device design concept with respect to initial clinical safety and device functionality. In general, feasibility studies are not designed or intended to generate statistically valid results. Therefore, 1) there will be no formal statistical hypothesis testing conducted, and 2) sample size is not based on power calculations.

This study is designed to gather information about the pressure waveform parameters during leak point pressure events in urodynamic testing. UDT data will be collected and analyzed to assess the changes and dynamic in LPP, UPP and other UDT parameters with and without acute PNS.

The results of this study may be used to design a statistically powered study to demonstrate safety and efficacy of the new therapy. A sample size of up to 15 will allow initial assessment of safety and improve understanding how LPP changes with acute PNS.

### 10.1 General Approach

In this study, only subjects that receive PNS will be included in the analysis. Study subjects that receive acute PNS and complete the UDT will be assessed for safety and evaluation of the changes in LPP and UPP with and without PNS. Study subjects that receive acute PNS and do not complete the UDT will be included in safety analysis only. Study subjects that do not receive acute PNS will be excluded from the study analysis.

Data analysis will comprise of descriptive statistics (means, standard deviations, correlations, etc.) on the outcome measures and variables listed in **Error! Reference source not found.** below.

The final report will include summary data and descriptive statistics of measurements performed in the study, including all Adverse Events and complications reported during the urodynamic test.

**TABLE 1: DATA SET VARIABLES**

Variables	
General	
 
Informed Consent (date, version, process)
 

Demographics	
 
Year of birth (age at time of test)
 
Gender
 
Ethnicity
 
Race
 
BMI (Height, Weight)
 

Medical history:	
 
Condition
 
Onset year
 

Urinary incontinence history:	
 
Type (SUI, UUI, MUI, Other)
 
Duration
 
Treatment
 
Severity (number of incontinence episodes/day)
 

Eligibility	
 
Inclusion criteria
 
Exclusion criteria
 

Neurostimulator	
 
Manufacturer
 
Model numbers of components
 
Indication
 
Stimulation setting/parameters
 
Electrode configuration
 

Urodynamic test*	
 
• Test date
 
• Post voiding residual
 
• Fill-in rate
 
• Bladder volume at 1st instability event
 
• Detrusor pressure at 1st instability event
 
• Bladder volume at leakage event
 
• Detrusor pressure at leakage event
 
• Max detrusor pressure during filling phase
 
• Max cystometric capacity
 
• Cough Leak Point Pressures (CLPP)
 
• Valsalva Leak Point Pressures (VLPP)
 

Neurostimulation settings	
 
• Existing neurostimulator settings
 
• Neurostimulator settings during setup and testing
 
• Patient sensations during stimulation, including the location and intensity of the sensation
 

Electromyography	
 
• Number of electrodes
 
• Location of electrodes
 

Urethral pressure profile (optional)	
 
• Urethral Closure Pressure Profile (UCPP)
 
• Maximum Urethral Closure Pressure (MUCP)
 

## 10.2 Safety Analyses

All subjects that received acute PNS will be included in the safety analysis. The rate of serious study related adverse events will be summarized as the number of events, the number of subjects with event and the percent of subjects with event within the safety population. There are no formal statistical hypothesis tests. Additionally, the number of all study related AE, the number of subjects with study related AE and the percent of subjects with AE will be summarized by type of event, severity, seriousness and relationship to the study.

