### 6.1 Number of subjects

Up to 15 subjects

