### 8.1.3 Potential Risks Associated with Acute Pudendal Nerve Stimulation

The harms in this category only include those related to changing the device settings to deliver stimulation in a slightly different way that is still within the allowable ranges of the approved neurostimulator device. The differences in stimulation settings may include greater amplitude, different pulse width, frequency and different electrode configuration. The risks associated with the implanted stimulation system already exist in these patients since they were already implanted for the current indicated PNS treatment and the incremental risk incurred due to participation in the study is only due to the temporarily changed stimulation settings.

The incremental risks a subject may experience during the study procedure due to adjustment of the electrostimulation parameters and the delivery of acute vs. continuous PNS are alphabetically identified below. The estimated probability of these risks occurring is More Frequent (occurring more than 10% of the time):

- Temporary discomfort due to high level of stimulation
- Temporary dysesthesia (abnormal sensation)

- Temporary pain

The incremental risks a subject may experience after the conclusion of the study procedure due to adjustment of the electrostimulation parameters and the delivery of acute vs. continuous PNS are alphabetically identified below. The estimated probability of these risks occurring is Rare (occurring less than 1% of the time):

- Discomfort due to high level of stimulation
- Dysesthesia (abnormal sensation)
- Pain

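### Study-related adverse events, a primary endpoint, are to be reported from at most 15 subjects without any interval, so the report will not show how little zero events rules out

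*Combined protocol and SAP*

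**What the plan says.** **Safety.** Section 5.2 makes the identification of study-related adverse events the first primary endpoint. Section 10.2 reports serious study-related events as the number of events, "the number of subjects with event and the percent of subjects with event within the safety population". For all study-related events it gives counts and percentages broken down by type, severity, seriousness and relationship.

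**LPP.** Section 10.1 states: "Data analysis will comprise of descriptive statistics (means, standard deviations, correlations, etc". The list is open-ended, but no interval is named in it or anywhere else.

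**Sample size and purpose.** Section 6.1 sets "Up to 15 subjects", with no minimum. Section 10 says that "sample size is not based on power calculations" and that "there will be no formal statistical hypothesis testing conducted". It also says: "A sample size of up to 15 will allow initial assessment of safety and improve understanding how LPP changes with acute PNS", and "The results of this study may be used to design a statistically powered study to demonstrate safety and efficacy of the new therapy".

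**Anticipated risks.** Section 8.1 sorts expected harms into three frequency classes: above 10%, 1% to 10%, and below 1%. Section 8.1.3 puts stimulation effects persisting after the procedure in the lowest: "Rare (occurring less than 1% of the time".

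**The concern.** The plan names two uses for the results: an initial view of safety and possible input to a powered study. Both need the reader to know how uncertain the estimates are, and the plan provides no measure of that.

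At n = 15 the percentage of subjects with an event moves in steps of 1/15 = 6.7%. A line showing 0% can look reassuring, yet it is compatible with a wide range of true rates. A line showing 6.7% can look alarming when it reflects one subject. An interval beside the figure guards against both misreadings.

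For LPP, a mean and standard deviation from a small and possibly selected set of pairs would be reported with no sign of how well either is estimated.

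**Working it through.** The documents give no precision figure, so there is none to reproduce. They also set no confidence level; two-sided 95% is assumed here.

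**Inputs.** n = 15 is the ceiling in section 6.1. The true n may be lower, since no minimum is set. It may also be slightly higher for safety: section 9.5 allows replacement of subjects who do not finish the test, and the cap may count only completers.

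**1. Zero events.** The exact upper limit is 1 − 0.025^(1/n).
- n = 15: 1 − 0.025^(1/15) = 1 − 0.782 = 21.8%
- n = 12: 26.5%
- n = 10: 30.8%
- n = 8: 36.9%
- n = 17 (two replacements above the cap): 19.5%

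The choice of method changes the n = 15 figure little: 18.1% for a one-sided 95% exact limit, 20.0% by the rule of three (3/15), 20.4% by Wilson.

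**2. One or two events at n = 15 (Clopper-Pearson, beta quantiles).**
- 1/15 = 6.7%, interval 0.2% to 31.9%
- 2/15 = 13.3%, interval 1.7% to 40.5%

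**3. Chance of seeing 0/15 for a true rate p, (1 − p)^15.**
- p = 1%: 86%
- p = 5%: 46%
- p = 10%: 0.9^15 = 21%
- p = 21.8%: 2.5%

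Zero events is the likely result at 1% and still a one-in-five result at 10%.

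**4. LPP mean and standard deviation, if one change per subject existed and were roughly normal.**
- Half-width of the 95% interval for the mean, in SD units, t(0.975, n−1)/√n: 0.55 at n = 15, 0.72 at n = 10, 0.84 at n = 8.
- Limits for the SD as multiples of the estimate, √((n−1)/χ²): 0.73 to 1.58 at n = 15, 0.69 to 1.83 at n = 10, 0.66 to 2.04 at n = 8.
- Required sample size scales with the variance, so at n = 15 the factor is 0.732² = 0.54 to 1.577² = 2.49.

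Fewer than 15 pairs is plausible. Section 9.1 admits up to eight subjects with no history of stress incontinence, which could leave 15 − 8 = 7 with it. Step 7.3.6 lets the stimulation-on assessment be skipped when no leak occurs with stimulation off. At n = 7 the SD multipliers are 0.64 to 2.20.

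**5. Illustration only.** Assume a later two-arm trial with LPP change as its endpoint, a difference of 0.5 observed SD, 80% power and two-sided 5%. The point estimate gives 63 per arm and the SD limits give 34 to 157. With 63 per arm, power is 43% if the true SD is at its upper limit. None of these design inputs is in the documents.

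**6. Denominator.** Sections 10.1 and 10.2 put everyone who received acute stimulation in the safety analysis. Section 11.6 describes safety reporting for eligible subjects who complete the urodynamic test under stimulation. A subject who stopped early because of an event would be counted under the first rule and lost under the second.

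**The case against.** The best defence is that this is an openly descriptive early feasibility study, and section 10 disclaims both hypothesis tests and a power-based size. That is true, but an interval is estimation: it requires no hypothesis and no larger sample, so the disclaimer does not argue against it.

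Several stronger readings are tempting and are not supported.
- *The percentages stand alone.* They do not. Section 10.2 prints the number of events and of subjects beside them, so a reader can compute the interval. The gap is one of reporting.
- *Zero events will be taken to confirm the risk classes in section 8.1.* Those classes are anticipated risks that inform the risk-benefit section. The plan does not make them benchmarks, and section 10 claims only an initial assessment.
- *The LPP standard deviation will be handed to the next trial.* Section 10 says the results may be used for design. It names no SD, no endpoint and no design, so power figures for that trial are illustrative.
- *Intervals are excluded for LPP.* The list in section 10.1 is open-ended; intervals are merely not committed to.

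Two practical objections stand. Intervals on every cell of the adverse event tables would mostly be very wide ranges around zero or one event, which is more than is needed. And the protocol defines no single LPP change per subject: section 7.3 and its notes allow several bladder volumes, repeats, changed settings and a skipped stimulation-on step; Table 1 lists cough and Valsalva values separately; and if stimulation stops the leak there is no stimulation-on value. A t interval on whatever pairs remain would describe a selected subset.

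**Conclusion.** The point holds as a cheap improvement of low severity. A primary endpoint will be reported from at most 15 subjects with no measure of precision, and zero events at n = 15 leaves true rates up to 21.8% open (30.8% at n = 10). These figures rest on a two-sided 95% exact limit, which the documents do not specify, and on independent subjects. Because 15 is a ceiling, the report must use the actual safety n.

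For LPP the conclusion is conditional. Once a per-subject change is defined, and if it is used to size a later trial, an SD from 15 pairs is uncertain by a factor of 0.73 to 1.58 under normality, and by more with fewer pairs. The documents do not support the claim that a later trial will be underpowered.

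**What to change.** **Section 10.2.** Report an exact (Clopper-Pearson) two-sided 95% interval for two quantities only: the percent of subjects with any serious study-related event and the percent with any study-related event. Use the actual number who received acute stimulation as denominator, after bringing section 11.6 into line with sections 10.1 and 10.2.

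**Section 10.** Add one sentence: if no subject has an event, true rates up to the computed upper limit remain possible (21.8% if the safety n is 15).

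**Section 10.1.** First define one stimulation-on minus stimulation-off LPP change per subject: which manoeuvre, which volume, which repeat and which setting, and how a leak abolished by stimulation is handled. Then report the number of evaluable pairs, the mean change with its t-based 95% interval, and the SD with its confidence limits. State that subjects without a paired leak are not represented.

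**Cost.** The safety part takes a few sentences and a few lines of code, with no new data or visits. The LPP part needs the definition first, which is more work. The downside is that the safety statement will look less favourable.

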### 10.2.1 Adverse Events (AE)

An Adverse Event (AE) is defined as any untoward medical occurrence in a study subject whether or not considered related to the study device, study procedures or study requirements that is identified or worsens during the study.

Adverse events must be assessed and documented by the investigator at the time of the study procedure visit.

The Investigator should institute appropriate therapeutic and follow-up measures in accordance with good medical practice and record them in the subject's medical history.

All AEs will be captured on the appropriate CRF. Information to be collected includes event description, time of onset, clinician's assessment of severity, relationship to study procedure (assessed only by those with the training and authority to make an assessment), and time of

resolution/stabilization of the event.

Any medical condition that is present at the time that the participant is screened will be considered as baseline and not reported as an AE. However, if the study participant's condition deteriorates at any time during the procedure visit, it will be recorded as an AE.

A list of possible risks associated with the study procedure are included in the section titled "Known potential risks" within this document.

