The purpose of real-time collaboration between study staff and Inspire is to make decisions about the best time points and/or bladder volumes to stop for leak point pressure testing, and whether leak point pressure testing should be repeated with stimulation off if no leaks are elicited with stimulation off. The representatives from Inspire may provide additional guidance, as needed, for troubleshooting and ensuring no important data collection is missed.

4. Follow-Up Phone Call

The third visit will take place by phone and will include assessment of any adverse events which may develop following the Stimulation Visit. This will take place 1 week (+/- 2 days) after the Stimulation visit.

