#### 10.2.5 Time Period and Frequency for Event Assessment and Follow-Up

The occurrence of (S)AE may come to the attention of study personnel during study visits, or upon review by a study monitor. All AEs occurring during the study must be documented appropriately regardless of relationship.

The Principal Investigator will record all reportable events with start dates occurring during the acute stimulation visit. All study related AEs will be followed until 7 days after the end of the study.

All SAEs, and UADEs will be followed until the event is resolved or until a final outcome is established by the Principal Investigator, or for no more than 30 days post the end of the study, whichever occurs first.

Device Deficiencies or Complaints related to any of the market released medical devices utilized during the study or during the clinically indicated procedure should follow standard reporting procedures applicable to device user facilities.

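### Section 10.2.1 gives two answers on whether a pre-existing condition that worsens after the stimulation visit is an adverse event

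*Combined protocol and SAP*

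**What the plan says.** Section 10.2.1 opens with a broad definition. An AE is any untoward occurrence, related or not, "that is identified or worsens during the study". Section 6.4 puts the end of the study at completion of the Visit 3 call, which section 6.3 schedules 1 week (+/- 2 days) after the stimulation visit.

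The same section then says that a condition present at screening "will be considered as baseline and not reported as an AE", and qualifies this with one case: "if the study participant's condition deteriorates at any time during the procedure visit, it will be recorded as an AE".

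Two other sentences are also tied to the visit. Section 10.2.1 says "Adverse events must be assessed and documented by the investigator at the time of the study procedure visit", and section 10.2.5 says "The Principal Investigator will record all reportable events with start dates occurring during the acute stimulation visit".

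Other text points the other way:
- Section 10.2.5 also says "All AEs occurring during the study must be documented appropriately regardless of relationship".
- Section 6.3 says the follow-up call "will include assessment of any adverse events which may develop following the Stimulation Visit", and the Table of Events (6.5) marks AE assessment at Visit 3.
- Section 10.2.3 classifies patient harm from lead polarity assignment or from adjusting stimulation current as a procedure-related AE. It sets no time limit and makes no exception for baseline conditions.

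**The concern.** Every subject enters with an implanted stimulator that has been in place for at least 3 months, so an existing, treated condition is to be expected. At Visit 2 the usual stimulation is switched off, amplitude is raised until discomfort and then reduced, and the previous settings are restored at the end (sections 3, 6.3 and 7.2). Some after-effects could therefore appear as a change in a symptom the subject already had. Section 8.1.3 itself lists "The incremental risks a subject may experience after the conclusion of the study procedure due to adjustment of the electrostimulation parameters", naming discomfort, dysesthesia and pain. In a subject who had one of these at screening, the same harm would present as worsening.

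The sentence that deals specifically with pre-existing conditions stops at the end of the procedure visit. Site staff who follow it as the specific instruction could treat later worsening as baseline. Staff who follow the definition would record it. Primary endpoint 1 is the identification of study-related AEs, so the count could depend on which sentence is applied, and could differ from one subject to the next.

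**Working it through.** The protocol states no figure that can be reproduced here: section 10 plans no hypothesis test and no power calculation. The check is to apply each rule to the same case.

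**Case A: a symptom present at screening, stable at Visit 2, worse two days later, reported at the Visit 3 call.**

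| Text | Result for case A |
|---|---|
| 10.2.1, AE definition, with 6.4 | AE: it worsened before the study ended |
| 10.2.1, baseline sentence | Not reported: present at screening |
| 10.2.1, exception for deterioration | Not met: the visit was over |
| 10.2.1, timing of assessment | Not covered: it was not present at the visit |
| 10.2.5, start-date sentence | Not covered: onset after the visit |
| 10.2.5, documentation of all AEs | Documented, if it is an AE |
| 6.3 and 6.5, Visit 3 assessment | Assessed |
| 10.2.3, harm from adjusting stimulation | Procedure-related AE, if that was the cause |

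No text says which row prevails.

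**Case B: the same worsening, but within Visit 2.** The definition and the exception both make it an AE. There is no conflict.

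**Case C: a new symptom two days after Visit 2.** The baseline sentence does not apply. The assessment-timing and start-date sentences exclude it, while the definition, the documentation sentence and Visit 3 include it. New post-visit events are therefore also subject to contradictory text. Case A differs from case C in facing one further obstacle, the baseline exemption. Amending the start-date sentence alone would settle case C but leave case A open.

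**Length of the disputed interval.** Visit 2 lasts about 90 minutes (section 3), or 1.5 h. Visit 3 falls 5 to 9 days later. The period under the definition, counted from the start of Visit 2, is 1.5 + 24 × 5 = 121.5 h to 1.5 + 24 × 9 = 217.5 h, against 1.5 h under the exception. This describes clock time only. It does not measure risk, because section 8.1.3 places most stimulation harm within the procedure (above 10% during, below 1% after).

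**Effect on the reported percentage.** Section 10.2 reports the percent of subjects with an event. With the maximum of 15 subjects, one unrecorded subject shifts this by 1/15 = 6.7 points and two shift it by 2/15 = 13.3 points. With fewer subjects the shift is larger. This applies where the subject has no other recorded event in the category.

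**The case against.** The strongest reply is that the text never says deterioration during the visit is the sole recordable kind. The baseline sentence can be read as saying that a stable condition is not itself an AE, with the next sentence giving one example of what is. The definition, the documentation sentence in 10.2.5 and the Visit 3 assessment would then make post-visit worsening an AE. Section 10.2.3 covers the most obvious case, harm from changed stimulation, without a visit limit. Most of this stands. It shows that capture is possible and probably intended. It does not remove the contradiction, because the sentence written for pre-existing conditions still points the other way.

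A reader might infer that post-visit worsening is certain to be excluded from primary endpoint 1 while new events remain fully covered. The documents do not support that. The passages just named allow worsening to be recorded, and the start-date sentence, read equally literally, would exclude new post-visit events too.

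A reader might also infer that the data must confirm the below-1% post-procedure figure in section 8.1.3. That is not shown: the documents do not say how many subjects have pain or dysesthesia at screening, and in subjects without them these would be new events.

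On size, the objection is that such events may be rare. If 1% is taken as an assumed rate from the upper edge of the section 8.1.3 post-procedure category, 15 subjects give 15 × 0.01 = 0.15 expected cases and a 1 − 0.99^15 = 14% chance of at least one. That is a fair caution, although the category refers to stimulation-related discomfort, dysesthesia and pain and not to worsening of bladder symptoms in general.

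**Conclusion.** The point holds as an internal contradiction. For a pre-existing condition that worsens between the end of Visit 2 and the Visit 3 call, section 10.2.1 gives opposite answers and nothing in the protocol ranks them. The consequence is possible under-recording, or inconsistent recording, of events that belong to primary endpoint 1 when judged study-related.

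No magnitude can be taken from the documents, because they give no rate of post-visit worsening and no indication of which reading staff would apply. What can be said is that with up to 15 subjects, one or two unrecorded subjects would visibly change the reported AE percentage. The study is descriptive, so no test or error rate is affected. The text should be corrected because the safety count is a primary endpoint and the correction is small.

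**What to change.** In section 10.2.1, replace the limit to the procedure visit in the deterioration sentence with: *from the start of the stimulation visit through completion of Visit 3*. In the same edit, bring two other sentences into line with the AE definition and the Visit 3 assessment: the 10.2.1 sentence on when AEs are assessed, and the 10.2.5 sentence that limits recording by start date.

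At the Visit 3 call, ask whether any existing condition is worse than before the stimulation visit. If so, record it as an AE and grade relatedness under 10.2.4. The medical and incontinence history in Table 1 supplies the list of conditions to ask about.

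The cost is a few sentences and a short enquiry at a call already planned. The downside is that some natural fluctuation in symptoms will be recorded as AEs and will need a relatedness grade, so the overall AE count may look somewhat higher. The relatedness categories in 10.2.4 allow such events to be separated from those attributed to the procedure.
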